#### **Clinical Global Impression CGI S (structured)**

*The CGI-S scale measures global severity of illness at a given point in time, and is usually rated on a 7-point, Likert-type scale ranging from 1 (normal, not ill at all) to 7 (among the most extremely ill patients). However, no version of the CGI-S exists which has been specifically adapted for use in AT patients; therefore, a 5-point version was developed that takes into account the severity of the following symptoms of AT: ataxia (walking), dysarthria, dysmetria, extrapyramidal symptoms (chorea, myoclonus, dystonia, and tremor), and eye movements. Ratings of none (0), mild (1), moderate (2), severe (3) and very severe (4) are selected based on the level of symptomatology. Two independent versions of the CGI-S scale were developed, a structured scale, based on the 5 disease-related anchors and an unstructured scale based on the clinical judgment of an experienced physician. Both the structured and unstructured versions were field-tested. The final structured CGI-S score is based on the severity of the symptoms in each domain, as indicated below:*

- *A rating of 0 (not ill/asymptomatic) can be made only if there are no symptoms, or a rating of mild on only one symptom domain;*
- *A rating of 1 (mild) can be made only if there are not more than 2 domains rated greater than mild;*
- *A rating of 2 (moderate) can be made only if there are not more than 2 domains rated greater than moderate;*
- *A rating of 3 (severe) can be made only if there are not more than 2 domains rated greater than severe;*

- *A rating of 4 (very severe) can be made only if there are at least 2 domains rated as severe and at least 2 rated as very severe.*

The final structured CGI-S score is captured on the “CGI-S” eCRF Form as “CGI-S overall rating”.

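### As worded, the structured CGI-S conditions permit no overall rating for 171 of the 181 domain profiles with three or more very severe domains

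*SAP*

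**What the plan says.** SAP 7.4.7 (CGI-S, structured) describes "a structured scale, based on the 5 disease-related anchors". The five anchors are ataxia, dysarthria, dysmetria, extrapyramidal symptoms and eye movements. The levels are: "Ratings of none (0), mild (1), moderate (2), severe (3) and very severe (4) are selected based on the level of symptomatology".

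The overall rating must then satisfy one of five conditions:

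- Rating 0 "can be made only if there are no symptoms, or a rating of mild on only one symptom domain".
- Rating 1 "can be made only if there are not more than 2 domains rated greater than mild".
- Rating 2 "can be made only if there are not more than 2 domains rated greater than moderate".
- Rating 3 "can be made only if there are not more than 2 domains rated greater than severe".
- Rating 4 needs "at least 2 domains rated as severe and at least 2 rated as very severe".

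Protocol 12.2 has the same conditions, so the SAP has carried them over. Neither document says what to do with a profile that meets none of them.

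The SAP takes the overall rating from the CGI-S eCRF form as the rater entered it and does not derive it from the domains. SAP 10.6.1 summarises it as a categorical variable on the FAS, repeats this by age and region, plots stacked bar charts, and lists the individual items. CGI-S belongs to the secondary objective in SAP 3.1 and to the exploratory objective in protocol section 8.

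**The concern.** The conditions for ratings 1 to 3 are ceilings: they limit how many domains may exceed the level. The condition for rating 4 is of another kind, because it asks for a minimum number of domains at severe as well as a minimum number at very severe. With only five domains, a patient who moves from severe to very severe on one more domain can lose the severe domains that rating 4 asks for, while already being over the ceiling for rating 3.

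Protocol 12.1.2 describes the disease as relentlessly progressive, treatment may run well past 12 months, and CGI-S is repeated every six months. A gap at the severe end lies in the direction of worsening. A rater who meets it must enter a value that the written conditions do not allow, or leave the field blank. Different raters may choose differently, and the SAP has no check of the overall rating against the domains. A blank also matters: under SAP 8.1 percentages are by default based on patients with data, so a patient too severe to be rated would drop out of the denominator and the severity distribution would look milder. SAP 8.2.1.2 refers missing data to section 7, which has no rule for a missing post-baseline CGI-S.

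**Working it through.** The documents give no figure on this point, so there is none to reproduce. The check lists every possible profile and applies the conditions as worded.

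**Inputs.** Five domains, five levels coded 0 to 4, and the five conditions above, all from SAP 7.4.7 and protocol 12.2. Number of profiles: 5^5 = 3125.

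**Step 1: where rating 3 and below are barred.** Rating 3 fails when three or more domains are very severe; ratings 0, 1 and 2 then fail too. Profiles with

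- exactly three very severe: C(5,3) × 4² = 10 × 16 = 160
- exactly four: C(5,4) × 4 = 20
- all five: 1

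Total: 160 + 20 + 1 = 181.

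**Step 2: which of these meet rating 4.** At least two domains must be severe and at least two very severe. With three very severe, both remaining domains must be severe: C(5,3) × 1 = 10 profiles. With four or five very severe, at most one domain is left, so none qualifies.

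**Step 3: the gap.** 181 − 10 = 171 profiles meet no condition: 150 of 160, 20 of 20 and 1 of 1. That is 171/181 = 94.5%. Every profile with two or fewer very severe domains meets at least the condition for rating 3, so the gap lies wholly in this region.

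**Step 4: non-monotonicity.** (3,3,4,4,4) meets rating 4. Worsening one domain gives (3,4,4,4,4), with four very severe and one severe, which meets nothing.

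**Step 5: other readings of rating 4.**

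- At least four domains severe or worse, of which at least two very severe: five very severe domains become ratable. Three very severe with both others below severe still meets nothing: 10 × 3² = 90 profiles.
- At least two domains severe or worse and at least two very severe, with very severe counting towards both: no profile is left out. All profiles with exactly two very severe domains, C(5,2) × 4³ = 640, then permit both 3 and 4.

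**Step 6: overlaps.** Ratings 2 and 3 are both permitted when at most two domains exceed moderate: 3^5 + 5 × 2 × 3^4 + 10 × 2² × 3³ = 243 + 810 + 1080 = 2133. A further 100 profiles permit only 3 and 4: two very severe with at least two of the other three severe, 10 × (1 + 3 × 3). Total with more than one permitted rating: 2233. Under the second reading in step 5 it is 2133 + (640 − 10 × 3³) = 2133 + 370 = 2503.

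**Step 7: effect of closing the gap.** Let rating 4 also be met by three or more very severe domains. Then 171 profiles gain a permitted 4 and none is unratable. Rating 4 is permitted for 110 + 171 = 281 profiles, where 110 = 10 + 100 are those permitted now. All 181 in step 1 permit 4 and nothing else. Worsening a domain never removes a permitted 4. The 100 profiles that permit both 3 and 4 are unchanged.

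**The case against.** The strongest reply is that the conditions do not compute the score. Each says when a rating can be made, so they constrain a clinician's global judgement. The analysed value is the rater's entry, raters are trained and certified on the CGI (protocol 12.4), and the scale was field-tested. This stands, and it limits the point: a value may well be recorded for every patient. It does not remove the gap, since for the 171 profiles any value entered breaches the written conditions. The pilot result in protocol 12.2 concerns mild, moderate and severe disease and does not mention the very severe category.

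Secondly, the threshold reading in which very severe counts towards both parts of rating 4 leaves no gap. That is correct, but neither document states it, and it raises the overlapping profiles from 2233 to 2503.

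Thirdly, profiles are not patients. The documents give no distribution of domain ratings. Protocol 7.3 says that speech and fine-motor problems usually stop progressing at about 12 to 15 years, and the phase II baseline ICARS averaged 50.6 of 100 (protocol 7.1.3.1). Neither shows how many patients reach three very severe domains. This stands: the number may be small or zero.

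Two stronger readings are tempting. One is that patients at the top of the scale cannot be validly scored. The documents do not support this, because 110 profiles may be rated 4 and the overall rating is recorded directly. The other is that the 2233 overlaps show a broken scale. They follow from conditions that are necessary and not sufficient, so overlap leaves room for judgement and is no error in itself.

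**Conclusion.** The rating 4 condition is wrong as written. Taken literally, the conditions leave 171 of 181 profiles with three or more very severe domains without a permitted rating, and they are non-monotone. This rests on reading severe in rating 4 as that level only. One looser reading leaves 90 profiles unrated and another leaves none, and the documents choose neither.

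The effect on results cannot be sized from the documents. The exposure is to inconsistent or missing ratings in the top categories of a descriptive secondary measure. The primary safety objective is not touched, and no hypothesis test depends on CGI-S. The correction is still worth making before the tables are run, because the domain items needed are already to be listed.

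**What to change.** Keep the recorded CGI-S overall rating as the analysed score, and in the SAP:

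1. State in 7.4.7 that the rating 4 condition is met when three or more domains are very severe, or when at least two are severe and at least two very severe as now written. Record this in section 3.6 as a SAP clarification, since the raters worked under the protocol wording and the change cannot alter ratings already made.
2. From the five recorded domain items, count and list by visit the assessments whose profile meets none of the conditions as now written, and those whose overall rating is missing or not permitted for the profile.
3. Repeat the CGI-S summary as a sensitivity analysis with every assessment that has three or more very severe domains set to 4. SAP 10.6.1.2, which now says that sensitivity analysis does not apply, needs a matching line.

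Do not derive the score as the lowest rating whose condition is met. That would score (4,4,1,1,1) as mild, because only two domains exceed mild, and would move 100 of the 110 profiles for which rating 4 is now permitted down to 3. Where several ratings are permitted, the rater's choice should stand.

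The cost is one extra CGI-S table and one listing, with no new data collection in this study. The OLE baseline comes from Visit 15 of IEDAT-02-2015 for patients who completed that trial, so extending the check to baseline needs the item-level CGI-S from that study. The documents do not say whether those items are transferred; if they are not, the check starts at the first post-baseline visit.

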### **EQ-5D-5L**

*A patient/caregiver-rated assessment of quality of life (QoL) will be performed using the EQ-5D-5L scale. The EQ-5D is a standardized instrument for assessing health-related QoL, which provides a simple descriptive profile and a single index value for health status in a variety of health conditions. The EQ-5D includes single item measures of five health dimensions: mobility, self-care, usual activities, pain/discomfort, and anxiety/depression. In addition, EQ-5D includes a global rating of current health using a visual analogue scale (VAS) ranging from 0 (worst imaginable) to 100 (best imaginable).*

*The EQ-5D-5L [...] includes five levels of severity (i.e., no problems, slight problems, moderate problems, severe problems, and extreme problems) for each of the five EQ-5D dimensions. These levels are scored from 1=no problems to 5= extreme problems. (EuroQol Research Foundation, 2019)*

*For children and adolescents, the EQ-5D-5L administrators will be trained to help the younger population in the study complete the scale. The EQ-5D-5L administrator will explain in detail the scale to the younger patients and will confirm that they understand how the scale should be completed. They will explain what each domain measures in a child friendly manner and will confirm that the respondent understands how to complete the scale. With regards to the usual activities’ domain, the administrator will explain that this domain measures if a subject has difficulties going to school, or with hobbies, sports, playing and doing things with family or friends. The administrator will be present during the completion and will be available to help the child if he/she does not understand a question or has questions related to scale completion. If the patient is unable to complete the scale, it will be completed by the patient’s parent/caregiver.*

Replies to the EQ-5D-5L questionnaire are recorded on the ‘Quality of Life (EQ-5D-5L)’ eCRF page.

### **EQ-5D-5L health state**

The scores (1-5) for the five dimensions are concatenated into a 5-digit code (in the order mobility, self-care, usual activities, pain/discomfort, and anxiety/depression) that describes the patient’s health state.

### **EQ-5D-5L index**

From the EQ-5D-5L health state the EQ-5D-5L index values are calculated based on the Crosswalk Value Set for the US. If one of the dimensions has a missing score, the EQ-5D-5L index value is derived as missing.

### **EQ-5D-5L index - change from OLE-IEDAT baseline**

The EQ-5D-5L index - change from OLE-IEDAT baseline is calculated at each relevant FU visit as:

- EQ-5D-5L index - change from baseline = EQ-5D-5L index at FU  
- EQ-5D-5L index at OLE-IEDAT baseline.

## 7.4.8 Safety Variables

### Adverse Events

*An adverse event (AE) is defined as any untoward medical occurrence in a patient or clinical investigation subject administered a pharmaceutical product and that does not necessarily have a causal relationship with this treatment. An AE can therefore be any unfavorable and unintended sign (including an abnormal laboratory finding), symptom, or disease temporally associated with the use of a medicinal (investigational) product, whether or not related to the medicinal (investigational) product.*

Adverse events data are collected from the time that informed consent is given until 30 days after the final visit (Month 12 or early discontinuation) or at least 60 days after final infusion, whichever is longer, on the 'Adverse Events' eCRF page.

The AE Description (Investigator term) is coded to a Lower-Level Term (LLT), a Higher Level Term (HLT), a Preferred Term (PT) and a System Organ Class (SOC) using MedDRA.

AEs' intensity is recorded as "Mild", "Moderate" or "Severe". any AE with a missing intensity is considered "Severe".

### Treatment-emergent adverse events (TEAEs)

A treatment-emergent adverse event (TEAE) is defined as an AE that started or increased in severity on or after the date of first Study Treatment Administration. All AEs that occur during this OLE-IEDAT study are defined as TEAE as all patients received study treatment in the IEDAT-02-2015 study.

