## 5. Data Preparation

### 5.1 Data Handling and Medical Coding

For data quality control, medical coding and data provided by third parties which is not contained in the clinical database (e.g., central lab, DSP concentrations, data coming from the ATTeST study for data reconciliation), please refer to the Data Management Plan, including the Data Validation Plan, in its most recent version.

ADaM datasets from the ATTeST study containing the treatment subgroups and the ATTeST baseline values are provided by EryDel.

Determination of Adverse Events of Special Interest (described in Section 7.4.8) is based on an Excel spreadsheet provided by EryDel documenting the outcome of a manual review of Adverse events contained within the clinical database.

For the definition of Adverse Events During COVID-19 treatment interruptions (described in Section 7.4.8) the times to be considered as treatment interruptions due to Covid-19 are provided by EryDel in form of an Excel spreadsheet.

The following coding dictionaries are used in the analysis:

MedDRA version 22.0 for Adverse Events, Medical History and Non-drug Therapies and Procedures. This comprises the datasets: 1) MH, 2) AE and 3) NDRP.

The verbatim event terms are coded to a Lower-Level Term (LLT), Preferred Term (PT), High Level Term (HLT), High Level Group Term (HLGT) and a System Organ Class (SOC). Only PT and SOC are used in the analysis.

WHO-DD version of March 2019 for Prior and Concomitant Medications. This concerns the dataset CM.

The Investigator Terms (Generic Medication Name, and Indication) are coded to a WHO-ATC Drug class, a WHO-ATC Drug number, a WHO Drug Name (Preferred Term) and Anatomic Therapeutic Chemical (ATC) level classification to all levels from 1 to 4.

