#### **Adverse Events During COVID-19 treatment interruptions**

For patients with treatment interruptions that result in gaps in dosing of greater than 60 days, adverse events are only considered treatment emergent if they occur within 60 days following the last dose. Adverse events that occurred greater than 60 days following the last dose will not be considered treatment emergent. For this population of patients whose long treatment interruption was due to COVID-19, three types of summarizations will be prepared:

- On dose (treatment emergent) adverse events
- Off dose (not treatment emergent) adverse events. Off dose events are those that occur during a period >60 days following a dose and prior to the immediately following dose.
- Restart (TEAE after restart of treatment) adverse events. Restart events are those that occur on/after the first dose after an off-dose period and prior to the start of any following off dose period.

Times to be considered as treatment interruptions due to Covid-19 are provided by EryDel in form of an excel spreadsheet.

|   |         |  |
|---|---------|--|
| CD+4 Lymphocyte count   | x10E9/L | Month 6 and Month 12   |
| Early morning Plasma Cortisol testing for Adrenal Insufficiency | µg/dL   | As needed: when patients are symptomatic, and when patients are at most risk for adrenal insufficiency and adrenal crisis, such as following discontinuation or interruptions of dexamethasone dosing |
| High dose ACTH stimulation test                                 | µg/dL   | As needed: In the event that patients show signs or symptoms of adrenal insufficiency during the study  |

All laboratory assessments are performed at local laboratories. Quantitative laboratory results are converted to their respective Reporting units for use in summary tables. Assessment of results as being within the normal range are made by the local laboratory. *Any laboratory abnormalities meeting the definition of an adverse event should be recorded on the Adverse Events CRF.*

Clinically notable values of standard laboratory are derived based on SI units as outline in Appendix 13.1.

If repeat tests are performed at any visit the result documented under the nominal visit label is used in all summaries and analyses for that Visit.

Baseline is as described in Section 7.1.

The change from baseline is calculated for quantitative laboratory tests at each scheduled post-baseline visit as:

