## 10.7 Safety Results

### 10.7.1 Adverse Events

#### Brief Summary of Adverse Events

An overview of AEs (including the number of patients with at least one TEAE, at least one TESAE, at least one TEAE leading to Death, at least one AESI, the number of patients who permanently withdrew the Study Treatment due to a TEAE, AEs during COVID-19 interruption, the worst intensity of any TEAE experienced by each patient with at least one TEAE and the closest relationship to Study Treatment of any TEAE experienced by each patient with at least one TEAE) is summarized for the SAF.

This summary is repeated for each 12-month period as described in Section 7.1.

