### Display of Adverse Events

Adverse events are summarized on a per-patient basis (i.e. if a patient reported the same event repeatedly the patient is counted only once at the specific level of display) and on a per event basis. Absolute counts (n) and percentages (%) are presented for the number of patients with at least one Adverse event, and per SOC and per PT within SOC, for the SAF. Percentages are based on the number of patients in the population.

Descriptive tables are ordered by descending frequency of the overall number of patients within each SOC, and then ordered within each SOC by the number of patients within each PT. In the event of equal frequencies, tables are ordered by number of events in the respective category and, in the event of a tie, alphabetically.

AEs are summarized for the SAF as follows:

- Treatment-Emergent Adverse Events
- Treatment-Related Treatment-Emergent Adverse Events
- Adverse Events of Special Interest
- Treatment-Emergent Adverse Events by worst intensity
- Treatment-Emergent Adverse Events leading to death
- Treatment-Emergent Serious Adverse Events
- Treatment-Emergent Adverse Events that led to discontinuation of Study Treatment.
- On dose Treatment-Emergent Adverse Events During COVID-19 Treatment Interruption.
- Off dose Treatment-Emergent Adverse Events During COVID-19 Treatment Interruption.
- Restart Treatment-Emergent Adverse Events After COVID-19 Treatment Interruption.

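### SAP 7.4.8 makes every extension-study AE treatment-emergent and elsewhere excepts off-dose AEs without linking the two rules; separately, the infusion dates drop late-started infusions that the SAF counts

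*SAP*

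**What the plan says.** **TEAE definition.** SAP 7.4.8 first ties treatment emergence to onset or worsening from first treatment onward. It then removes any limit: "All AEs that occur during this OLE-IEDAT study are defined as TEAE as all patients received study treatment in the IEDAT-02-2015 study". It names no exception.

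**COVID-19 interruptions.** A later subsection of 7.4.8 opens with "For patients with treatment interruptions that result in gaps in dosing of greater than 60 days" and continues: "Adverse events that occurred greater than 60 days following the last dose will not be considered treatment emergent". It sets three classes: on dose (treatment-emergent), off dose (not treatment-emergent) and restart (treatment-emergent). An off-dose event must fall more than 60 days "following a dose and prior to the immediately following dose". A restart event must fall on or after the resuming dose and "prior to the start of any following off dose period". Section 5.1 adds that "the times to be considered as treatment interruptions due to Covid-19 are provided by" the sponsor in a spreadsheet.

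**Outputs.** The overview in 10.7.1 lists "AEs during COVID-19 interruption" alongside the TEAE counts. The list of AE displays includes "Off dose Treatment-Emergent Adverse Events During COVID-19 Treatment Interruption". In section 12.1 the off-dose table (14.3.1-1.10) omits the treatment-emergent label, while the on-dose and restart tables (14.3.1-1.9 and 14.3.1-1.11) carry it.

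**Infusion dates.** SAP 7.1 counts an infusion toward the first or last infusion date only if the eCRF question about starting within 30 minutes of the EDS process is answered Yes. The Safety Analysis Set (6.1) needs only a performed date on the infusion page. The number of infusions (7.4.6) counts every completed infusion.

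**The concern.** TEAEs, including serious AEs and discontinuations due to AEs, are part of the primary endpoint (SAP 3.4), and section 9 plans analyses to support a New Drug Application. Serious, discontinuation, treatment-related and fatal events are each derived in 7.4.8 as subsets of TEAEs, so any ambiguity in the TEAE flag passes to all of those tables. Adverse events of special interest come from a manual review of all AEs, but under headings that say TEAE. They are affected only so far as they are restricted to TEAEs.

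Two programmers following the SAP could produce different headline counts. One applies the blanket sentence and keeps off-dose events in the main tables. The other treats the COVID-19 subsection as an exception and removes them.

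The infusion-date rule raises a different problem. A patient can belong to the safety set on the strength of an infusion that does not count when Study Day, the 12-month AE periods and treatment duration are derived.

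**Working it through.** The plan gives no figure to reproduce here. The first check compares the two TEAE rules day by day; the second applies the date rules to simple infusion records.

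**A. TEAE rules**

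Let *d* be whole days since the last dose and *g* the gap between doses.

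- TEAE definition: every AE is a TEAE at any *d*.
- COVID-19 subsection: if *g* > 60, an AE is a TEAE only when *d* ≤ 60.
- The rules disagree from *d* = 61 to *d* = *g* − 1, which is *g* − 61 days.

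The documents give no gap lengths, so those below are assumptions, except that 76 = 2 × 38 is one missed infusion at the SAP's longest permitted interval.

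| Gap (days) | Days in dispute | Share of gap |
|---|---|---|
| 38 | 0 | 0% |
| 61 | 0 | 0% |
| 76 | 76 − 61 = 15 | 20% |
| 90 | 90 − 61 = 29 | 32% |
| 180 | 180 − 61 = 119 | 66% |
| 365 | 365 − 61 = 304 | 83% |

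*Scope.* One missed infusion on the 21–38 day schedule gives a gap of 2 × 21 = 42 to 2 × 38 = 76 days. If the cause is not COVID-19, up to 15 days are in dispute when the subsection's first sentence is read as covering any gap, and none when it is confined to the sponsor's list.

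*Never restarted.* The off-dose class requires a next dose. SAP 7.4.1 says Indian sites were terminated because of COVID-19, so some patients may have stopped during an interruption and not resumed. For them a late AE is a TEAE by the definition, not a TEAE by the subsection's second sentence, and outside the off-dose class as worded. An off-dose event that itself leads to permanent withdrawal falls into the same hole, because no dose follows it. AEs are collected until the later of 30 days after the final visit and at least 60 days after the final infusion. For illustration, an assumed discontinuation visit 90 days after the last dose gives collection to day 120, so days 61–120 (60 days) have no clear class.

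**B. Infusion dates**

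Duration (7.4.6) is last date − first date + 1. Take infusions on days 0, 28, 56 and 84.

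- All started on time: 84 − 0 + 1 = 85 days.
- First started late: the first date becomes day 28, and duration is 84 − 28 + 1 = 57 days.
- Last started late: the last date becomes day 56, and duration is 56 − 0 + 1 = 57 days.
- Only infusion started late: the patient is in the safety set but has no first date, last date, Study Day or duration.

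With the first infusion late, an AE on true days 0–27 gets a Study Day from −28 to −1. The first AE period starts at day 0, so the event falls in no 12-month interval. On the 21–38 day schedule, the displaced time is 21/365 = 5.8% to 38/365 = 10.4% of the true first 365 days.

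For 12 infusions at 28-day spacing, a late first or last infusion cuts duration from 11 × 28 + 1 = 309 to 10 × 28 + 1 = 281 days (28/309 = 9.1%). The infusion count stays at 12.

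In the Non-switch Placebo group the same restricted date is the first active infusion (7.1), so the 6-month efficacy windows move too.

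**The case against.** The best defence of the TEAE rules is that a general rule and a specific exception can coexist. The COVID-19 subsection labels its own classes, and the table titles in 12.1 follow them. Its heading, its summaries and the sponsor's spreadsheet all point to COVID-19 interruptions only. This defence largely stands. A reader might infer that the two rules cannot both be applied, and the documents do not support that. What remains is that the definition says all AEs without qualification, 10.7.1 contradicts the subsection's label, and the overview does not say whether off-dose events leave the TEAE counts.

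It can also be argued that a patient who stops for good has discontinued rather than been interrupted, so only the definition applies. That is a reasonable answer, but the SAP does not give it.

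A reader might also see a conflict for AEs on days 61–67 after the final infusion, inside the safety follow-up window of days 53–67. That needs a strained reading. In context the last dose is the one before the gap, an off-dose period needs a following dose, and the restart class makes such an event a TEAE, as it is in a patient without a gap.

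On infusion dates, the protocol requires infusion within 30 minutes of the EDS process, so a late start would be a deviation and may be rare. Without the eCRF, a No answer beside a performed date could mean a late infusion or none at all. That lowers confidence in this part, and the fix must not count infusions that were not given.

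**Conclusion.** The TEAE point holds as a missing link between a rule and its exception, plus one wrong label and one unassigned group. The main TEAE, serious, discontinuation and fatal TEAE tables change with the rule programmed. The disagreement is confined to AEs more than 60 days after a dose in patients with gaps over 60 days. The number of such patients is not given, and the days in dispute rest on assumed gaps.

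The infusion-date point holds on the text at lower confidence. It matters only if an infusion was given, the 30-minute question was not answered Yes, and that infusion was the patient's first or last. A reader might infer that it also changes which AEs are TEAEs. It does not, because the blanket sentence does not depend on that date.

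Nor do the documents support a claim that safety data are lost. The study is descriptive, off-dose events have a planned table, and 10.7.1 lists all AEs, serious AEs and AEs with outcome death. Both points should be fixed.

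**What to change.** 1. In the TEAE definition (SAP 7.4.8), add to the blanket sentence an exception for off-dose AEs as defined in the COVID-19 interruption subsection. State that this single flag feeds Tables 14.3.1-1.1.1 to 14.3.1-1.8. Leave the rest of the definition unchanged, so that no second first-dose anchor is introduced.
2. In the COVID-19 subsection, limit the first sentence to the interruptions on the sponsor's list, to match its heading and summaries. Assign a class to AEs more than 60 days after the last dose in patients who never restart.
3. In 10.7.1, delete the treatment-emergent label from the off-dose display.
4. In 7.1, define the first and last OLE infusion dates as the earliest and latest performed date on which an infusion was actually given, by the same criterion as the Safety Analysis Set and regardless of the 30-minute answer. Check against the eCRF what a No answer means. Report late starts as deviations. This concerns analysis dates only and implies nothing about how infusions should be timed.

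The cost is SAP wording, one reprogrammed flag and two date derivations. All the dates needed are already collected.
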